### **Objective:**

The primary objective is to estimate and compare the prevalence of major structural defects in siponimod exposed pregnant women versus 1) disease-matched pregnant women not exposed to siponimod, and 2) healthy pregnant women.

Secondary objectives are to estimate and compare the prevalence of selected adverse pregnancy and infant outcomes in siponimod-exposed pregnant women versus 1) disease-matched pregnant women not exposed to siponimod, and 2) healthy pregnant women.

The primary outcome of the study is major structural defects.

The secondary outcomes of the study are:

- Spontaneous abortion
- Stillbirth
- Elective termination
- Preterm delivery
- Preeclampsia / eclampsia
- Small for gestational age infants
- Small for age for postnatal growth to one year of age
- A pattern of minor structural defects
- Developmental performance at approximately one year of age
- Serious or opportunistic infections in the first year of life.

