## **Variables**

Exposure will be defined as siponimod treatment any time from the first day of the last menstrual period (LMP) prior to conception + 4 days up to and including the end of pregnancy by maternal report and verified by medical record review, with detailed information on the gestational timing, route of administration, dose, and dates of exposure. Outcome variables include major structural birth defects (including interventions for those defects and outcome up to one year of age), spontaneous abortion, stillbirth, elective termination, preterm delivery, minor structural defects, small for gestational age at birth, small for age on postnatal growth at 1 year of age, developmental performance on the Ages and Stages (ASQ) questionnaire for live born infants at 1 year of age, and serious or opportunistic infections in live born infants through the first year of life. Data will be obtained by maternal report, physical examination, and medical record review. Potential confounders or covariates to be collected include maternal age, race/ethnicity, socioeconomic status, body mass index (BMI), pregnancy and health history, lifestyle factors such as tobacco and alcohol use, comorbidities, medication, vaccine and vitamin/mineral exposures, and prenatal tests. Measures of disease severity will be collected for those enrolled in the siponimod-exposed and disease-matched cohorts. Details regarding definitions will be provided in the Statistical Analysis Plan (SAP) to be developed separately.

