## 6 Research question and objectives

The purpose of the Siponimod Pregnancy Exposure Registry is to evaluate the effect of siponimod exposure on rates of pregnancy and infant outcomes in exposed pregnancies compared to unexposed disease-matched and healthy unexposed pregnancies. The lack of human fetal safety data for siponimod makes such a monitoring system an important component of epidemiologic research on the safety of this drug.

The primary objective is to estimate and compare the prevalence of major structural defects in siponimod exposed pregnant women versus 1) disease-matched pregnant women not exposed to siponimod, and 2) healthy pregnant women.

The primary objective will be evaluated among i) pregnancies ending in at least one live birth, and ii) pregnancies ending in at least one live birth, spontaneous abortion, still birth or termination of pregnancy

Secondary objectives are to estimate and compare the prevalence of selected adverse pregnancy and infant outcomes in siponimod-exposed pregnant women versus 1) disease-matched pregnant women not exposed to siponimod, and 2) healthy pregnant women.

Mayzent exposure is defined as exposure to siponimod any time from the 4th days post the first day of LMP prior to conception up to and including the end of pregnancy.

- The primary outcome of the study is major structural defects.
- The secondary outcomes of the study are:
  - Spontaneous abortion/miscarriage
  - Stillbirth
  - Elective termination
  - Preterm delivery
  - Preeclampsia / eclampsia
  - Pattern of 3 or more minor structural defects
  - Small for gestational age
  - Postnatal growth small for age at approximately one year of age
  - Developmental performance at approximately one year of age
  - Serious or opportunistic infections in the first year of life.

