Elective termination / abortion	Outcome – secondary	Maternal report Medical record	A deliberate discontinuation of pregnancy through medication or surgical procedures.
Premature delivery	Outcome - secondary	Maternal report Medical record	A spontaneous or induced delivery at <37.0 gestational weeks (as counted from LMP), reported by the mother and validated through the medical record.
Preeclampsia / Eclampsia	Outcome - secondary	Maternal report Medical record	Reported by maternal interview and confirmed with medical records.
Small for gestational age	Outcome - secondary	Maternal report Medical record	Birth size (weight, length or head circumference) $\leq 10^{\text{th}}$ percentile for sex and gestational age using National Center for Health Statistics (CDC, 2000) pediatric growth curves for full term infants. Prenatal growth curves specific to preterm infants will be used for premature infants (Olsen, 2010).
Postnatal growth deficiency	Outcome - secondary	Medical record	Postnatal size (weight, length or head circumference) $\leq 10^{\text{th}}$ percentile for sex and age using NCHS pediatric growth curves (CDC, 2000), and adjusted postnatal age for premature infants.
Screening for Developmental Milestones	Outcome - secondary	Neurodevelopmental questionnaires	Screening for neurodevelopment performed using the Ages and Stages Questionnaire (ASQ). An abnormal score is defined in the scoring guidelines.
Serious or Opportunistic Infections	Outcome - secondary	Maternal report Medical record	Defined as tuberculosis, x-ray proven pneumonia, neonatal sepsis, meningitis, bacteremia, invasive fungal infection, pneumocystitis, septic arthritis, osteomyelitis,

Variable	Role	Data source(s)	Operational Definition
			abcess (deep tissue), and infections requiring hospitalization, identified in live born infants up to one year of age.
Maternal Age (years)	Confounder	Maternal report	Maternal age (years) at due date, continuous and categorical (<25, 25-29, 30-34, >34).
Paternal Age (years)	Confounder	Maternal report	Paternal age (years) at due date, continuous and categorical (<25, 25-29, 30-34, >34).
Maternal Race	Confounder	Maternal report	Maternal (Caucasian/White, Black, Asian/Pacific Islander, Native American, Other).
Maternal Ethnicity	Confounder	Maternal report	Maternal (Hispanic, Non-Hispanic).
Maternal Education	Confounder	Maternal report	Maternal Educational Category (years of completed education <12, 12-15, >15).

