#### **7.4.3.4 Medical records and general pediatric evaluation**

Upon completion of the outcome interview, each woman will be mailed a packet containing research HIPAA compliant medical records release forms for the delivery hospital, obstetrician, pediatrician, and specialty physician, if applicable. For women whose pregnancies have ended in spontaneous abortion, elective termination or stillbirth, records release forms will be mailed for prenatal diagnosis, pathology or autopsy reports if available. Each woman will be asked to sign the medical records release forms, as well as [REDACTED] HIPAA Authorization Addendum (if they or their child receives medical care at [REDACTED]), and to return these authorization documents along with the pregnancy exposure diary form.

Upon receipt of the signed medical records release forms, a standard physical evaluation form will be mailed to each pediatrician or other physician responsible for the care of each live born infant. This form includes information on infant size at the time of the latest examination and an open-ended question about postnatal complications including major structural defects and serious or opportunistic infections as defined in this protocol.

At one year of age, another research HIPAA compliant medical records release form for the pediatrician or healthcare provider caring for the child is sent to the mother for signature, and the signed form with a standard physical evaluation form is sent to the healthcare provider to request updated information on growth, major structural defects, and any serious or opportunistic infections as defined in this protocol up through one year of age.

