- **Postnatal growth deficiency:** postnatal growth deficiency is defined as postnatal size (weight, length or head circumference) less than or equal to the 10th centile for sex and age using National Center for Health Statistics (NCHS) pediatric growth curves, and adjusted postnatal age for premature infants if the postnatal measurement is obtained at less than one year of age (CDC, 2000).
- **Screening of Developmental Milestones:** one or more domains scored as abnormal on the Ages and Stages Questionnaire completed by the mother when the infant is approximately one year of age will define achievement of developmental milestones.
- **Serious or Opportunistic Infections:** serious or opportunistic infections are defined as any one or more diagnoses of tuberculosis, x-ray proven pneumonia, neonatal sepsis, meningitis, bacteremia, invasive fungal infection, pneumocystitis, septic arthritis, osteomyelitis, abscess (deep tissue), and infections requiring hospitalization identified in live born infants up to one year of age.

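### Postnatal growth deficiency has two age-correction rules for preterm infants, and the Section 7.7.2.4 rule switches at the endpoint's own time point of about 12 months

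*Protocol*

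**What the plan says.** Two places in the protocol define the outcome operationally. Table 7-1 in Section 7.3 takes size at or below the 10th "percentile for sex and age using NCHS pediatric growth curves (CDC, 2000), and adjusted postnatal age for premature infants", with no upper age for the adjustment. Section 7.7.2.4 sets the same cut-off, "less than or equal to the 10th centile for sex and age using National Center for Health Statistics (NCHS) pediatric growth curves", but limits the adjustment: "adjusted postnatal age for premature infants if the postnatal measurement is obtained at less than one year of age".

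The time point varies slightly in wording but always centres on the first birthday. Section 6 has "Postnatal growth small for age at approximately one year of age", the Variables part of the abstract has "small for age on postnatal growth at 1 year of age", and the objectives in the abstract have "Small for age for postnatal growth to one year of age". Section 7.7.3.1.2 analyses weight, height and head circumference separately at about one year, in live born infants, with multiples excluded.

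Measurements come from the infant's own physician. Section 7.4.3.4 says of the evaluation form sent after the outcome interview: "This form includes information on infant size at the time of the latest examination". A second request, for growth up through one year, starts when the child reaches one year. Neither request carries a window around 12 months.

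**The concern.** The two definitions agree for every term infant and for a preterm infant measured before the first birthday. They disagree for a preterm infant measured on or after it: Table 7-1 as written corrects the age and Section 7.7.2.4 does not. The protocol does not say which text governs.

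Section 7.7.2.4 also has a difficulty of its own. Its switch sits at the age at which the outcome is meant to be assessed, so the reference age for a preterm infant jumps by the full prematurity lag at the first birthday. Two infants of the same gestational age and the same size can be classified differently because of their visit dates.

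The direction is known. Size norms rise with age in infancy, so omitting the correction can only move a preterm infant towards deficient. Preterm delivery is itself a secondary outcome, so a cohort difference in preterm delivery could carry over into the growth comparison. The gestational-age covariate in Table 7-1 is weeks at enrollment, not at birth, so it would not clearly remove this.

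**Working it through.** The protocol states no rate, power or sample size for postnatal growth deficiency, so there is no figure of its own to reproduce. The check compares the two rules on one case and then bounds the size of the discrepancy.

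**One case.** Take birth at 32 weeks and, as an assumption, correction counted from 40 weeks, a lag of 40 − 32 = 8 weeks.

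| Age at visit | Reference age, Table 7-1 | Reference age, Section 7.7.2.4 |
|---|---|---|
| 51 weeks | 43 weeks | 43 weeks |
| 53 weeks | 45 weeks | 53 weeks |

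Under 7.7.2.4 a two-week difference in visit date moves the reference age by 53 − 43 = 10 weeks. At 36 weeks' gestation the lag is 4 weeks and the jump is smaller.

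**Inputs.**
- Live births per cohort: 231 (Section 7.5.1). Check: 289 × (1 − 0.10 − 0.05 − 0.05) = 231.2, which agrees.
- Preterm rate in comparators: 10% (Table 7-4).
- Preterm rate in exposed, for illustration: 10% × 1.9 = 19%, using the detectable relative risk in Table 7-4.
- Flagged share with correction: 10%. This assumes that infants follow the reference curves once age is corrected.
- Shift *s*, in SD units, from using uncorrected age: not in the protocol. Assumed range 0.1 to 0.8.
- Every preterm infant is taken as measured at or after one year, which makes the results upper bounds for each *s*.

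**Formulas.**
- Share of preterm infants flagged without correction: x = Φ(−1.2816 + s).
- Extra infants per cohort at 10% preterm: 231 × 0.10 × (x − 0.10).
- Cohort prevalence at 10% preterm: 0.90 × 0.10 + 0.10 × x.
- Risk ratio from the rule alone, with no true growth effect and 19% against 10% preterm: (0.81 × 0.10 + 0.19x) / (0.90 × 0.10 + 0.10x).

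| s | x | Extra infants per 231 | Cohort prevalence | Risk ratio |
|---|---|---|---|---|
| 0.1 | 11.9% | 0.4 | 10.2% | 1.02 |
| 0.2 | 14.0% | 0.9 | 10.4% | 1.03 |
| 0.5 | 21.7% | 2.7 | 11.2% | 1.09 |
| 0.8 | 31.5% | 5.0 | 12.2% | 1.16 |

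For example, at s = 0.5 the extra infants are 23.1 × 0.117 = 2.7, and the risk ratio is (0.081 + 0.0413) / (0.090 + 0.0217) = 0.1223 / 0.1117 = 1.09.

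So about 2 to 21 in every 100 preterm infants measured at one year or later would change status between the two rules. They are the infants whose size lies between the two 10th centiles; the rest are classified the same either way.

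**The case against.** The strongest reply is that the table entry is a summary and Section 7.7.2.4 qualifies it. On that reading there is no contradiction, only a detail that the short entry omits, and Section 7.3 says that further definitional detail will follow in the SAP. This is a fair reading of how the two texts arose. It does not remove the problem, because following 7.7.2.4 as the governing text still leaves a rule that changes at the endpoint's own age.

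A reader might go further and infer that preterm infants seen at one year are misclassified as growth deficient, with Table 7-1 the correct rule. The documents do not support that. Nothing in the protocol ranks the two definitions or says that correction beyond 12 months is the right standard; the supportable word is inconsistent. Nor are preterm infants affected as a group: many keep the same status under both rules, and measurements before the first birthday are corrected under both.

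Other points also stand. The latest-examination wording describes the form sent after the outcome interview, so it does not by itself show measurements past 12 months; it shows only that no window fixes them. The 19% preterm rate is a detectable-effect figure, not an expectation. Excluding multiples removes some preterm infants. Births nearer 37 weeks shift less: if the assumed shift were 0.15 to 0.3 SD, the flagged share would be about 13% to 16% and the risk ratio about 1.03 to 1.05. No passage suggests that age at the one-year measurement will differ between cohorts.

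**Conclusion.** The inconsistency is real and narrow. Table 7-1 and Section 7.7.2.4 give different reference ages for a preterm infant measured at or after 12 months, and the 7.7.2.4 switch falls where the endpoint is assessed, with no stated window. The direction is towards more preterm infants called deficient, and it would be differential only if preterm delivery differed by cohort.

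The numerical effect is probably small. The extra infants are an upper bound at each assumed shift, since all preterm infants are taken as measured late. The risk ratios further require preterm delivery of 19% against 10%. Table 7-4 lists a detectable relative risk of 1.9 for endpoints with a 10% baseline at 231 per group, so a distortion of this size would be hard to tell from chance. The point is minor: it concerns a secondary outcome and is worth fixing because the choice between rules should not be made after outcomes are known.

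**What to change.** Before the final analysis, give Table 7-1 and Section 7.7.2.4 one classification rule that does not change at 12 months within the endpoint's measurement window. The simplest way is to delete the conditional clause from 7.7.2.4, so that adjusted age applies to all infants born before 37.0 weeks at the measurement used for this outcome, as Table 7-1 reads. Then state the measurement window for the one-year assessment and carry the same wording into the SAP.

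The cost is one clause and one added sentence. It should need no new data: date of delivery and gestational age are already collected, and both existing definitions already require age at measurement.

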#### 7.7.2.5 Lost-to follow-up

Subjects will be considered *lost-to-follow-up* if they have completed the initial intake interview but subsequently fail to complete the outcome interview despite a minimum of 13 telephone attempts and attempt to contact by mail as per study procedure manual within 1 year of the mother's estimated due date.

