### **7.4.3.2 Interim interview I and II (~20 and 32 weeks' gestation)**

Following the initial intake interview, participants will be sent a pregnancy exposure diary on which they will be asked to record any additional exposures (medications, vaccinations, vitamins, etc.) or events as the pregnancy progresses. Along with the pregnancy exposure diary, each woman will be sent a copy of the written informed consent document, and a research HIPAA compliant obstetric medical record release form.

Women who have enrolled in the study prior to 18 weeks post-LMP will be interviewed by telephone at 20-22 weeks post-LMP, 32-34 weeks post-LMP and within 0-6 weeks after the expected due date. Women who have enrolled between 18 and 20 weeks post-LMP will be interviewed at 32-34 weeks post-LMP and within 0-6 weeks after the expected due date.

Women who enrolled after 20 weeks post LMP and before 30 weeks post-LMP will be interviewed at 32-34 weeks post-LMP and within 0-6 weeks after the expected due date. Women who have enrolled after 30 weeks post-LMP will be interviewed within 0-6 weeks after the expected due date (See [Table 7-2](#)).

The purpose of these interviews will be to update records of pregnancy exposures and results of prenatal tests, to remind women to maintain the pregnancy exposure diary, to update phone number and address information, and to determine if the pregnancy has ended prior to the expected due date.

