### 7.4.3.7 Procedure and consequences for subject withdrawal

As stated in the informed consent, any study participant may withdraw from the study at any time for any reason; however, data that have been collected up to the time of withdrawal may be used. Women who withdraw from the study after the collection of birth outcome will not be considered lost-to-follow-up. Women who withdraw from the study prior to the collection of birth outcome will be considered lost-to-follow-up and the statistical analysis plan addresses the method whereby these data will be addressed.

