### 7.4.4 Data collection schedule

Data will be collected according to the schedule described in Table 7-2 below. After oral informed consent, a maternal telephone interview is conducted. Depending on the gestational age at enrollment, up to two additional telephone interviews are scheduled in the second and third trimesters of pregnancy. Written informed consent is requested following the intake interview.

- An outcome telephone interview is planned for 0-6 weeks after delivery
- After the end of pregnancy, research HIPAA compliant medical records release forms for the obstetric provider, delivery hospital, pediatrician, and any specialty care provider for the indicated disease, are sent to the mother for signature. Once the record release forms are received, records are requested from the providers and upon their receipt, data are abstracted.
- A one-year pediatric evaluation release form will be sent to the mother and once signed will be used to request data from the pediatric care provider.
- Between birth and approximately one year of age (or as soon as the examination can be practically arranged), a dysmorphology examination will be scheduled.
- When the child of the participant is approximately one year of age, the participant will be asked to complete the ASQ for her child.

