#### **7.7.2.3 Exclusion criteria for the primary outcome – major structural defects**

- Defects will be excluded based on criteria outlined in the CDC coding list as outlined in [Section 7.7.2.2](#).
- ***Time period for identification:*** structural defects ascertained after 12 months of age will not be included in the primary analysis, but will be considered separately in the context of a possible pattern.
- ***Defects identified in spontaneous abortions/miscarriage, stillbirths or elective terminations/abortions:*** defects identified by prenatal ultrasound or examination of the products of conception following elective or spontaneous abortion/miscarriage or stillbirth will not be included in the primary analysis of the primary outcome due to potential bias involved in non-uniform use of prenatal diagnosis and pathology evaluation for all abortuses; however, these defects will be included in the additional analysis of the primary outcome that includes all defects in the numerator over all pregnancies enrolled in the prospective cohort with known outcome in the denominator (excluding lost-to-follow-up).

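### Section 7.7.2.5 ties loss to follow-up to the outcome interview alone, so a pregnancy outcome documented in a medical record can be excluded or censored

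*Protocol*

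**What the plan says.** **Definition.** Section 7.7.2.5 classes women as lost to follow-up "if they have completed the initial intake interview but subsequently fail to complete the outcome interview despite a minimum of 13 telephone attempts" and an attempt by mail, all within one year of the due date. An outcome known from another source is not mentioned.

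**Use in the analyses.**
- In 7.7.2.3 the additional analysis of major defects places all defects "over all pregnancies enrolled in the prospective cohort with known outcome in the denominator (excluding lost-to-follow-up"). Section 7.7.3.1.1 repeats that exclusion for the second risk ratio.
- In 7.7.3.1.2 a woman lost before 20 weeks is right-censored in the spontaneous abortion analysis. Stillbirth and premature delivery are to be analyzed similarly.

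**Other statements on the same matter.**
- Section 7.4.3.7 uses a different test for withdrawals: "Women who withdraw from the study prior to the collection of birth outcome will be considered lost-to-follow-up". It leaves their handling to the SAP.
- Section 7.9 states an intention to follow up through healthcare providers. It describes the secondary defect analysis as covering every pregnancy whose outcome is known.

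**Access to records.**
- After intake, under 7.4.3.2, "each woman will be sent a copy of the written informed consent document, and a research HIPAA compliant obstetric medical record release form".
- Section 7.4.3.4 sends the later forms after the interview: "Upon completion of the outcome interview, each woman will be mailed a packet containing research HIPAA compliant medical records release forms for the delivery hospital", as well as for the obstetrician, pediatrician and any specialty physician.
- Section 7.4.4 ties them to a different event: "After the end of pregnancy, research HIPAA compliant medical records release forms for the obstetric provider, delivery hospital, pediatrician" and specialty provider are sent to the mother.

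**The concern.** A missed interview and an unknown outcome are different things. The obstetric release goes out after intake, so the registry may hold a record of a miscarriage, termination or prenatally detected defect for a woman who never completes the outcome interview. Under 7.7.2.5 she is still lost. The protocol then uses known outcome and not lost to follow-up as if they described the same women.

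The exclusion could be informative if women with a loss or an affected infant are less willing to be interviewed. The documents give no evidence on this either way. The point matters because defect counts are small, so a few discarded outcomes are visible in the estimate. If 7.4.3.4 governs the mailing of releases, a missed interview also means that delivery and infant records are not requested, which leaves the provider follow-up in 7.9 with little to work on.

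**Working it through.** **1. The texts side by side**

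| Section | What decides whether the outcome counts |
|---|---|
| 7.7.2.5 | Outcome interview completed |
| 7.4.3.7 | Birth outcome collected (women who withdraw) |
| 7.7.2.3 | Outcome known, and not lost to follow-up |
| 7.9 | Outcome known |
| 7.7.2.2 | Defect identified by the mother or by provider/medical record, up to one year |
| 7.7.2.4 (preeclampsia) | Medical record alone is enough |

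Take a woman with a record-documented miscarriage and no outcome interview. Her outcome is known under 7.9 and on the record-based logic of 7.7.2.2 and 7.7.2.4. She is lost under 7.7.2.5. In 7.7.2.3 she meets one half of the condition and fails the other. In 7.7.3.1.2 she is censored although the event is on file.

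**2. The plan's own figures**

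Inputs from 7.5.1: 289 enrolled per cohort, 10% spontaneous abortion/stillbirth, 5% elective abortion, 5% lost.
- Known outcomes: 289 × (1 − 0.05) = 274.6, against 273 stated.
- Live-birth pregnancies: 289 × (1 − 0.10 − 0.05 − 0.05) = 231.2, against 231 stated.

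Both reproduce closely enough.

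**3. Ceiling on the number affected**
- Lost per cohort: 289 × 0.05 = 14.45.
- Live births among them, at 85%: 14.45 × 0.85 = 12.3.

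Only women with a usable release and an outcome on record could be recovered. The documents give no figure for that share.

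**4. Size for major defects**
- Expected comparator defects (3%, Table 7-4): 231 × 0.03 = 6.9.
- Expected defects among the lost live births at the same 3%: 12.3 × 0.03 = 0.37 per cohort.
- One discarded defect would equal 1/6.9 = 14% of the comparator count, but fewer than one is expected unless lost women carry a higher risk.

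Illustration on an assumed risk: retained risk is 3% in both cohorts, lost comparator births also have 3%, and lost exposed births have m times 3%. The analyzed risk ratio is 1.00. The full-cohort ratio is (231 + 12.3m)/(231 + 12.3).

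| m | Full-cohort risk ratio |
|---|---|
| 1 | 1.00 |
| 2 | 1.05 |
| 3 | 1.10 |
| 5 | 1.20 |

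**5. Size for spontaneous abortion/stillbirth**

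Expected events are 289 × 0.10 = 28.9. The loss risk among lost women is an assumption:
- at the planned 10%, 14.45 × 0.10 = 1.4 events per cohort;
- at 20%, 2.9 events (10% of 28.9);
- at 40%, 5.8 events (20% of 28.9).

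These are ceilings, because they assume that every such event is on record.

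**6. Size for power**

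If nobody were lost, live-birth pregnancies would be about 289 × 0.85 = 246 per cohort, a generous bound. Power of the two-sided Fisher test at 3% versus 9% moves from 74.0% (231 per group) to 77.1% (246 per group). The gain is at most about 3 percentage points.

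**The case against.** The strongest reply is that the protocol means outcome unknown whenever it says lost. Section 7.5.1 obtains its known outcomes by removing the 5% lost, and 7.7.2.3 pairs the two terms. Section 7.4.3.7 concerns women who withdraw, not women who cannot be reached, and its handling is left to a SAP that is not shown. Loss is expected to be low (7.9), and lost and retained women will be compared. A woman who ignores 13 calls and a letter may not return a release form either.

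Much of this stands as a limit on size. It does not cure the definition: 7.7.2.5 is the only operational rule for women who cannot be reached, and it names only the interview. Comparing characteristics does not recover outcomes.

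A reader might infer four stronger things that the documents do not support:
- *That these women drop out of every analysis.* Section 7.7.3.1.2 keeps them as right-censored in the time-to-event analyses. The live-birth primary comparison in 7.7.3.1.1 carries no explicit exclusion for loss to follow-up.
- *That delivery and infant records can never be obtained.* This follows from 7.4.3.4 but not from 7.4.4, and an obstetric release has already gone out after intake.
- *That about 14 women per cohort have recoverable outcomes.* That number is everyone lost.
- *That the rule biases the cohorts differentially.* It is the same in all three. The expedited reports in 9.2.1 on exposed pregnancies run from the Research Center to the sponsor and are not planned as an extra source of outcomes.

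**Conclusion.** The point holds as a defect in a stated rule. Applied as written, 7.7.2.5 excludes or censors pregnancies whose outcome the registry may already hold, and this conflicts with the known-outcome wording and record-based ascertainment used elsewhere. The different release timing in 7.4.3.4 and 7.4.4 is a separate inconsistency that affects how often the problem arises.

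The size is modest at the planned 5% loss: at most about 14 women or 12 live births per cohort, with about 0.4 defects expected among those births at 3%. It would be larger if loss exceeds 5%, is related to outcome or differs between cohorts. The risk-ratio shifts of 1.05 to 1.20 and the 1.4 to 5.8 losses rest on assumed risks among lost women and on complete recovery from records. A change is worth making because it is cheap, and because releases are hard to obtain once a woman is out of contact.

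**What to change.** 1. In 7.7.2.5, define lost to follow-up as no pregnancy outcome from either the outcome interview or a medical record within one year of the due date, after the contact attempts already listed. Apply it identically in all three cohorts.
2. State in 7.7.2.3, 7.7.3.1.1 and 7.7.3.1.2 that record-only outcomes enter the denominators and count as events.
3. Align the test in 7.4.3.7 with this definition. Women who withdraw stay outside further data collection, as 8.3.5 provides.
4. Reconcile 7.4.3.4 with 7.4.4 so that sending release forms does not depend on a completed outcome interview. The packet mailed after intake or the 32-34 week contact could carry them.

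**Cost.** An amended definition, an earlier mailing of existing forms and some extra record requests. Record-only cases will lack the late-pregnancy exposure and covariate updates that the outcome interview collects. The imputation in 7.7.3.2 covers missing confounders and uncertain spontaneous abortion dates, not missing exposure, so it meets this only in part. Reporting the number of record-only outcomes by cohort would show how much rests on them.
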